## Project Summary

Working memory refers to the active mental retention of information, to its manipulation, and to its use in guiding behavior. Its role in many types of high level cognition, as a factor underlying individual differences across a broad spectrum of experimental and “real world” measures, and as a factor in many psychiatric and neurological diseases, makes it important to many branches of cognitive and clinical neuroscience. The motivation for the experiments described in this protocol comes from previous findings from the PI’s group suggesting that an active neural representation of a stimulus may result from its attentional selection, rather than from its storage, *per se*, in working memory. More specifically, multivariate pattern analyses (MVPA) of data from three types of experiment – functional magnetic resonance imaging (fMRI), electroencephalography (EEG), and combined EEG and transcranial magnetic stimulation (TMS) – have failed to find evidence for the active retention of information that is in working memory, but outside the focus of attention. These are intriguing results, which suggest that the brain may use a “passive”, structural trace to hold information in working memory. If true, this fact would require a reconsideration of over 50 years of dogma about how working memory “works”. However, caution is warranted, because these recent findings are subject to two important qualifications: First, they comprise a set of null results; Second, each was acquired with a noninvasive method that is inherently limited in spatial and temporal resolution. The motivation for the experiments proposed in this protocol, therefore, is to overcome the inherent limitations of the studies summarized above by employing a physiological method, electrocorticographic (ECoG) recording from neurosurgical patients, that features spatial and temporal resolution that are far superior to those of fMRI or EEG. Specifically, adoption of ECoG for these new studies will enable a test of the hypothesis that a mechanism of phase-encoded selection among multiple active representations may underlie the attentional prioritization of one among many items held in working memory. A similar mechanism has recently been discovered, from ECoG data recorded during performance of a hierarchical cognitive control task, by a group working at the University of California. Addressing this question will require two sub-studies. First, a study of attentional selection with a well-characterized behavior that have previously been studied with both extracranial EEG and with ECoG. The specific question that this study will address is how the dynamics of oscillations in the alpha band differ when a location in space is being actively attended vs actively ignored vs not relevant for the task. Understanding this fundamental question will be important for interpreting the results from the second sub-study: working memory with attentional prioritization cues. These newly proposed experiments fit with the Aims of the parent project and thus their findings may also have translational relevance for the diagnosis and treatment of psychiatric disorders that are associated with abnormal neural oscillations.

## Background and Significance

Since at least the time of Hebb [26] it has widely been assumed that the short-term retention of information (a.k.a. “working memory storage”) is accomplished via maintenance of an active memory trace. This view has been reinforced by reports of elevated delay-period activity in extracellular [22], electroencephalographic [68], and hemodynamic [9, 11] recordings of animals and humans. Consequently, the loss of sustained activity is thought to indicate a disruption of the memory trace [15, 40, 56]. However, to date, virtually all studies of the short-term retention of information (regardless of species, procedure, concurrent physiological measurement, etc.) have confounded memory with attention. That is, the information to be remembered is the most task-relevant information throughout the memory interval, and therefore is likely to be continuously attended to. In a recently published study using functional magnetic resonance imaging (fMRI), the PI’s group unconfounded attention and memory by prompting endogenously triggered shifts of attention away from items that were being actively retained during a brief memory delay [33]. The results of the MVPA indicated that only items within the focus of attention elicited an active neural trace. Activity corresponding to the representation of items outside the focus of attention (i.e., UMs) quickly dropped to baseline. Nevertheless, this unattended information remained in working memory, because it could support near-perfect recognition at the end of the trial. (This finding was replicated conceptually with a different task, and different subjects, reported in the same paper [33].) In follow-up analyses with the same dataset, the PI’s group has shown that this finding holds even if analyses are restricted to putatively “category specific” regions

of interest (ROIs) identified with standard univariate methods (i.e., a GLM) [37]. Notably, head-to-head comparison of BOLD signal intensity levels vs. the information contained in this signal (as inferred from MVPA) indicates that direct interpretation of the former can be misleading: 1) activity levels are not always sensitive to which items are in vs. out of the focus of attention (nor, indeed, to which are in vs. out of a trial's stimulus set); and, 2) activity levels in a “category-specific” ROI can remain elevated above baseline even when the MVPA indicates the absence of information related to this category (Fig. 2). This second finding has been extended to the level of item representation in two other fMRI studies from the PI's group, in which frontal and parietal regions show sustained delay-period activity, but MVPA indicates that this activity does not represent which of 3 or 4 directions of motion is in memory [17, 58]. Reminiscent of previous findings [24, 62], however, trial-specific stimulus information was found to be represented during the delay period in early visual areas whose activity was not above baseline levels [17, 58].

The results presented up to this point lead to a hypothesis of considerable significance for theoretical and mechanistic accounts of working memory: Sustained delay-period activity may correspond to the focus of attention, rather than to working memory storage. At the theoretical level, confirmation of this hypothesis would require revision of models of working memory as the temporary activation of long-term memory (LTM) representations (e.g., [10, 44]). Importantly, formal implementations of this cognitive model in computational simulations do not treat “activation” as only a metaphor, but rely on it as a central explanatory factor (e.g., [46-48]). At the level of systems and cognitive neuroscience, confirmation of this hypothesis would call into question the near-universal assumption that working memory storage is supported by sustained activity in the brain. Evidence for this hypothesis comes not only from the PI's laboratory, but also from event-related potential (ERP) [52] and behavioral studies [49] of the control of attentional search with information in working memory. Based on these studies it has been theorized that a (active) “search template” and (passive) “accessory memory items” exist in two different states within working memory [49]. Independently, the PI's group and this “attentional search” group [49] have each suggested that unattended information within working memory might be represented in a short-lived pattern of synaptic weights – i.e., a structural code analogous to that used for LTM. Such a scheme has precedence in several computational models (e.g., of short-term recall of serial order [6, 8, 21] and retrieved context models [27, 61]). Unlike LTM, however, the physiological basis of this encoding scheme would not be long-term potentiation and -depression. Instead, it would be supported by a short-lived phenomenon, such as GluR-1-dependent short-term potentiation [20], or a transient increase in the presynaptic concentration of calcium ions [41]. Either of these mechanisms represents a neurobiologically plausible way that the brain could temporarily retain information for subsequent translation back into neural activity (i.e., for reinstatement into the focus of attention) by reactivation with a retrieval cue [42]. Increasingly, this idea is moving out of the realm of the hypothetical and into the empirical. For example, evidence for a role for so-called “silent synapses” in the transient storage of information has been reported from recordings in the PFC of monkeys performing a visual working-memory task [63], and short-term synaptic plasticity is a central feature of many neurobiologically oriented computational models of working memory [reviewed in 3]. Further, a transient, network-based mechanism exploiting the principles of matched-filter processing has also been proposed to support the short-term retention of visual information in inferotemporal cortex [64], one implication being that this general mechanism need not be assumed to be a PFC-specific phenomenon. (Relatedly, the PI's group has recently published behavioral data consistent with the idea that UMs may not be held in LTM [30].)

To be able to fully interpret the results from a study addressing the questions summarized in the previous experiment, however, it will first be important to improve our understanding the neurophysiological correlates of attentional selection, *per se*. In the extracranial EEG, the allocation of spatial attention to one region of the visual field is associated with a decrease in alpha-band activity in the cortical region representing the attended location, and an increase in alpha-band activity in the opposite hemisphere [71]. What's less clear, however, is whether alpha-band oscillations are elevated for all cortical regions that aren't representing the selected region of space, or, alternatively, only in regions that are implicated in the task, because they were potential targets prior to the onset of the

attentional cue. This is, formally, equivalent to the distinction between attended memory items, unattended memory items, and trial-irrelevant items [31, 35].

#### Specific Aims/Study Objectives:

Working memory refers to the active mental retention of information, to its manipulation, and to its use in guiding behavior. Its role in many types of high level cognition [e.g., 1, 18, 28], as a factor underlying individual differences across a broad spectrum of experimental and “real world” measures [e.g., 13, 23, 57], and as a factor in many psychiatric and neurological diseases [e.g., 2, 4, 19], makes it important to many branches of cognitive and clinical neuroscience. Since the mid 1990s, a popular and productive method for studying human working memory has been functional neuroimaging, including functional magnetic resonance imaging (fMRI). R01 MH095984, however, was motivated by two developments that called for alternative approaches to the study of working memory. The first was the growing evidence, from human and nonhuman electrophysiological studies, that oscillations in field-level electrical potentials play a critical functional role in the short-term retention of information in working memory [50, 65]. fMRI is inherently unable to measure such oscillatory activity. The second development was work from the PI’s laboratory indicating that, under some conditions, fMRI signal does not carry stimulus-related information across the delay-period of working memory tasks [33]. This finding, derived from highly sensitive multivariate pattern analyses (MVPA), challenged the widely held assumption that the short-term retention of information is necessarily based on a rate code (detected by fMRI as an increase in the BOLD signal), and provides further motivation for investigating the role of neural oscillations in working memory. It also led to Specific Aim 1 of R01 MH095984: To test the hypothesis that delay-period oscillatory activity carries stimulus-specific information. Five experiments were proposed under this Aim and, to date, Experiment 1 has been completed and published [31], and preliminary results that address Experiment 2 [60] and Experiment 3 [32] have been obtained. Each of these studies (to be detailed in the Significance section) addressed a special case of Specific Aim 1, which is the retention of information in working memory when that information is not in the focus of attention (“unattended memory items”, UMI).

The present protocol is motivated by the fact that the work summarized in the Background and Significance section point to two possibilities: a) It may truly be the case that UMIs are not represented by elevated neuronal activity; or, alternatively, b) UMIs are represented by elevated activity that occurs at too fine-grained a scale to be detected with noninvasive imaging methods. Adjudicating between these two possibilities will require an invasive technique that allows for recording neural signals that relate directly to the “elevated activity” that is at the heart of this question. Thus, to continue to make progress on the core question of the neural bases of stimulus representation in working memory, this Revision Application has been prepared to propose pursuing the following “supplement to Aim 1”:

The Specific Aim of this project is to test the hypothesis, with electrocorticography (ECoG) recorded from neurosurgical patients, that unattended memory items (UMIs) are represented in phase angle-segregated patterns of activity in the high-gamma band (80-150 Hz), and that attentional prioritization within working memory is implemented via a mechanism of phase-encoded selection.

This novel hypothesis derives from a recent discovery, with ECoG, from patients performing a task that required the simultaneous maintenance of multiple stimulus-response (S-R) mapping rules: Different rules were found to be represented in prefrontal cortex (PFC) in patterns of high-gamma activity centered on different phase angles of the underlying theta oscillation, and selection among these rules was implemented by dynamic shifts in the phase angle of theta-band coherence between the PFC (where the rules were stored) and M1 (where they were implemented) [70]. Here, we are proposing that analogous mechanisms of phase-segregated representation and phase-encoded selection may also govern the attentional prioritization of one from among multiple items held in working memory.

#### Research Design and Methods:

##### General design considerations: Recruitment.

Subjects will consist of patients between the ages of 18 and 65 admitted to the UW Comprehensive Epilepsy Program who have undergone surgical implantation of subdural electrode arrays to better define their seizure focus. Inclusion Criteria: All patients with implanted electrode arrays who are willing to participate and able to cooperate and follow research instructions will be recruited. Exclusion criteria

include: IQ < 85; impairment of reading, naming, or articulation (determined by review of neuropsychology test results that are part of the patient's medical record); no cerebral pathology affecting the cortical regions from which recordings are made (determined by the neurosurgeon at the time of electrode implantation, and/or by the epileptologist who performs the clinical reading of the ECoG signals).

Recruitment will be carried by the PI's study team personnel: [name], [name] or [name]. They will routinely come to Epilepsy monitoring unit to identify patients that are potential subjects for the study in consultation with [name] or the Epileptologist. [name], [name] and [name] will have valid access to patient medical records, granted by UWHC. Once identified, a member of the PI's research team will approach the patient for participation, explaining the study procedures.

Informed consent will be obtained on the day of the consult during which the patient and physician decide whether the patient will undergo invasive EEG monitoring. A member of the study team will be present at that time to answer any questions the patient may have.

General design considerations:

Sub-study A:

This task will proceed in two phases: receptive field mapping and the attention task. For both, the display consists of four light gray circular apertures arranged in a square, one in each quadrant of the screen, and all equidistant from a central fixation point (a black "x", with one arm pointing to each aperture); the background is a uniform gray field. For Receptive Field Mapping, the subject will be asked to fixate the fixation point while black and white checkerboards are presented sequentially, for 500 msec each with a 500 msec inter-stimulus interval, in randomly determined order, in each of the four apertures. Independent of the checkerboards, the fixation symbol will unpredictably change from an "x" to a "+" on average once every 5 sec (range 4-6 sec), and subjects will be asked to report each change with a button press. This will be carried out in three 1-min blocks, each featuring 15 presentations in each of the locations during each block, for a total of 3 min of task. (Length of pauses between blocks will be determined by the patient.) Immediately upon the conclusion of the Receptive Field Mapping (when the patient is ready) the Attention Task will be explained to the patient. Each trial begins with two arms of the fixation "x" changing color for 300 msec, with green indicating the aperture in which it is 75% likely that a target will appear, and white the aperture in which it is 25% likely to appear. After a variable cue-target interval (CTI) of 800-1200 msec, the target, a grating of parallel lines that will either be tilted slightly to the left or to the right of vertical, will appear for 33 msec, followed by a screen asking "L or R tilt?", to which the subject responds with a left- or right-handed button press. The intertrial interval will last for 600 msec. Because subjects will be instructed to make their decision as quickly as possible, it is expected that the average trial will last just under 3 sec. Each block will consist of 48 trials (approximately 2min 24 sec), and within a given block, only two opposing locations of the four possible locations will be cued, the other two positions serving as task-irrelevant locations, at which a target will never appear within that block. The two cued positions will be changed every block. To maximize sensitivity for data analyses, we'll hope to acquire a total of 8 blocks worth of data (384 trials), which, without rests, would come to 19 min 12 sec. With rests between blocks, the entire session is expected to take between 25-30 min. (Note that whereas the 3 min of Receptive Field Mapping are necessary for interpreting the data from this study, as few as four blocks of data from the Attention Task would produce the minimal amount of data needed, and so if subjects fatigue or otherwise ask to terminate testing prior to completion of the full set of 384 trials, we will nonetheless have collected a sufficient amount of data within approximately 15 min of data collection.)

Sub-study B: Behavioral task, ECoG recording, and data processing.

Experimental procedure. The study consists of two sessions on different days. The generic task design will be as follows: In the first session, each trial begins with a fixation cross and serial presentation of two sample items, followed by a brief delay (Delay1pre-cue), followed by a cue (Cue1) indicating which item will be tested first, followed by an additional delay (Delay1post-cue), followed by a memory probe

requiring a “same/different” response (Probe1) followed by Delay2pre-cue, Cue2, Delay2post-cue, and Probe2. The timing will be as follows: Fixation (.5 sec); Sample1 (.5 sec); ISI (.1 sec), Sample2 (.5 sec); Delay1pre-cue (.5 sec), Cue1 (.5 sec), Delay1post-cue (2.5 sec), Probe1 (2 sec); Delay2pre-cue (.5 sec); Cue2 (.5 sec); Delay2post-cue (2.5 sec); and Probe2 (2 sec). Thus, total time per trial = 12.6 sec. (Note that the duration of the Delaypost-cue epochs is necessitated by the fact that behavioral [31, 45] and EEG data [31] indicate that it takes between 1-2 sec for an item to transition from AMI to UMI.). This timing will allow for the collection of 96-106 trials within a span of 30 min, a block that can be interrupted and restarted as needed to suit the comfort of the patient. (Previous experience from ECoG studies performed by colleagues of the PI who are based at the University of California indicates that the “20-min mark” is a conservative estimate of the duration of a testing session that a patient can be expected to tolerate; many patients can tolerate either longer sessions, or multiple sessions separated in time.) Critically, the ECoG study that discovered and characterized the phase-encoded selection mechanism that we will investigate in the present study [70] made this discovery in data from four patients, with a design that yielded 40-50 trials/condition/patient; thus our design, intended to collect a minimum of 96 trials, will be adequately powered to detect effects of interest at the single-subject level. (SNR of ECoG signals will be considered further along in this section.)

In the second session, each trial begins with a fixation cross and the presentation of one sample item, followed by a delay, followed by a rating test from 1 to 5 on how well the patient remembered seeing the sample in the first session. The timing will be as follows: Fixation (.5 sec); Sample (.5 sec); Delay (2.5 sec); Test (2 sec). Thus, total time per trial = 5.5 sec. Again, this timing will allow for the collection of 384 trials within a span of 35 min.

The practical aspects of the testing is that it will take place at least two days postoperatively, and only if the attending physician indicates that the patient is lucid and sufficiently comfortable that s/he could participate in two roughly 30 min-long sessions of cognitive testing. The test stimuli will be presented on a laptop computer, which will rest on a computer tray that is help up by a tripod-mounted adjustable arm. Thus, the computer can be positioned in whatever way that the patient finds most comfortable. Testing will occur at a time of day of the patient’s choosing, so long as this time conforms with the treatment schedule in the inpatient ward, and it is at minimum of one hour after the time that the subject would routinely wake up in the morning and a minimum of one hour prior to the time that the subject would routinely go to sleep.

We will be prepared to test patients with stimuli drawn from any of three domains: scenes; faces; and words. Note that, because we have observed the phenomenon of the absence of MVPA evidence for UMLs across many stimulus domains – direction of motion, phonology, semantics, faces, line orientations – we assume that principles governing the interaction of attention with working memory representations will be comparable across these domains. It is important to note that our assumption about where in the brain we will find neural correlates of the short-term retention of stimulus representations in working memory is grounded in the sensorimotor-recruitment model of working memory storage. This model posits that the short-term retention of stimulus information in working memory is supported by the very same neural circuits that are responsible for sensory/perceptual and/or motoric representation of this information in tasks that make no overt mnemonic demands. The growing body of evidence for, and theoretical implications of, this model have recently been reviewed by the PI in [12, 53-55].

For each stimulus domain, each sample stimulus will only appear once in the experiment. The stimuli were determined from previous studies using similar tasks to yield 75-90% correct performance in an independent set of healthy young adults. On each trial, two stimuli from the three categories will be presented, and cuing will be randomly determined, such that on each trial one item serves as the AMI, one as the UML, and one as the “irrelevant” category (i.e., the category that was not presented on that trial).

- Face stimuli will be photographs of highly discriminable faces with different genders and races. The probe stimuli will either be a same face, or a difference face with the same gender and race.

- Scene stimuli will be photographs of highly discriminable natural scenes. The probe stimuli will either be a same scene, or a difference scene from the same scene category.
- Word stimuli will be words that have homonyms. The probe stimuli will either be the homonym of the sample word, or a different word.

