#### Statistical Considerations:

Sub-study A: The analyses will proceed in two stages. The first will be to determine the spatial selectivity of each ECoG electrode by calculating its response, in high-frequency (70-250 Hz) broadband power to each of the four locations stimulated during the Receptive Field Mapping task. Also of interest will be fluctuations in alpha-band power (8-13 Hz), and in phase-amplitude coupling (PAC) between alpha-band oscillations in the ECoG signal and high-frequency broadband power.

Data analysis from the Attention Task will focus on electrodes identified in the Receptive Field Mapping task to be preferentially responsive to one, or a subset, of the four critical locations. For each of these electrodes, values of alpha-band power and PAC will be analyzed as a function of attentional condition: attended (i.e., cued with 75% likelihood); ignored (i.e., cued with 25% likelihood); or irrelevant. Although a recent study has looked at alpha-band power as a function of attended vs. ignored [14], the proposed study will differ from this in two important ways. First, our critical comparison is between ignored vs. irrelevant; second, all conditions in our task will be within the same informational domain and sensory modality (i.e., visuospatial perception), whereas that of [14] spanned both (i.e., it used switches between an auditory and a motor task). Because this previous study collected 190 trials per subject [14], we believe that our design, which will collect a total of 384 trials, will be sufficiently powered to carry out the analyses of interest.

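### Sub-study A: the critical ignored-versus-irrelevant contrast has no hemifield control, and on the ordinary reading of opposing cue pairs it mixes task relevance with hemispheric alpha lateralisation

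*Combined protocol and SAP*

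**What the plan says.** Research Design and Methods, Sub-study A, describes "four light gray circular apertures arranged in a square, one in each quadrant of the screen". Within a block "only two opposing locations of the four possible locations will be cued, the other two positions serving as task-irrelevant locations". One arm of the fixation symbol turns green and another white: "green indicating the aperture in which it is 75% likely that a target will appear". The white arm marks the second cued location, where the target probability is 25%. The green location is the attended one and the white location the ignored one. Between blocks, "The two cued positions will be changed every block". The section does not say whether opposing means diagonal, left-right or upper-lower. It gives no block sequence and no split of green between the two cued positions. It plans 8 blocks of 48 trials and accepts 4 blocks as the minimum.

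Background and Significance reports, from extracranial EEG, that spatial attention lowers alpha in cortex representing the attended location and brings "an increase in alpha-band activity in the opposite hemisphere". It then asks whether alpha is raised for everything outside the selected region, or only where a target had been possible.

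Statistical Considerations, Sub-study A, states that "our critical comparison is between ignored vs. irrelevant". Alpha power and phase-amplitude coupling are to be analysed by attentional condition (attended, ignored, irrelevant), in electrodes that favour one location or several. Neither section matches, stratifies or adjusts for whether the electrode's location shares a hemifield with the attended one.

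**The concern.** The contrast is meant to isolate task relevance: both locations are unselected, but a target can appear at only one of them. That works only if the two conditions are alike in other respects that move alpha. The protocol itself names one such respect, the hemisphere in which attention is represented. If the ignored location lies across the vertical midline from the attended one more often than the irrelevant locations do, a lateralisation effect enters the contrast.

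On the diagonal or left-right reading the bias makes ignored exceed irrelevant. That is the pattern expected if alpha rises only where targets were possible, so pure lateralisation could be read as support for that account. The Project Summary says the answer matters for interpreting the working-memory sub-study, so the error would carry forward.

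**Working it through.** **The plan's own figures.** 8 × 48 = 384 trials, and 8 × 2 min 24 s = 19 min 12 s. Both reproduce.

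**Inputs.** From the protocol: four locations, one per quadrant; two cued per block; 48 trials per block; 8 blocks planned, 4 the minimum. Assumed: green falls equally often on each member of a pair, blocks divide equally over the pairs used, and the electrode responds to one quadrant.

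**Counts for one electrode, diagonal pairs (two pairs, 4 blocks each).** Its location is in the cued pair in 4 × 48 = 192 trials: 96 attended and 96 ignored. In the other 192 trials it is irrelevant.

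- Ignored: the attended location is the diagonal partner, always in the opposite hemifield. Share opposite = 96/96 = 100%.
- Irrelevant: the cued pair is the other diagonal, with one end in each hemifield. Share opposite = 96/192 = 50%.

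At 4 blocks the counts are 48/48 and 48/96, so the shares are the same.

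**Bias.** Let d be alpha at the electrode with attention in the opposite hemifield minus alpha with attention elsewhere in the same hemifield. Suppose task relevance has no effect. Then

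ignored − irrelevant = (share opposite when ignored − share opposite when irrelevant) × d.

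| Cued pairs used | Ignored, opposite | Irrelevant, opposite | Bias |
|---|---|---|---|
| Diagonal only | 100% | 50% | +0.5d |
| Left-right only | 100% | 50% | +0.5d |
| Diagonal and left-right equally | 100% | 50% | +0.5d |
| Left-right and upper-lower equally | 50% | 75% | −0.25d |
| Upper-lower only | 0% | 100% | −d |
| All six pairs equally | 67% | 67% | 0 |

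Eight blocks do not divide equally over six pairs, and the word opposing does not describe such a mix. With diagonal pairs, if unequal cueing moved the irrelevant share to 40% or 60%, the bias would be 0.6d or 0.4d.

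**Illustration of size.** The documents give no d. Assume independent trials, trial SD 1, a two-sided 5% test and diagonal pairs. The standard error is √[1/96 + (1 + d²/4)/192]. For d = 0.4 it is √(0.01042 + 0.00542) = 0.126, and 0.2/0.126 = 1.59. The chance of a spurious rejection is then about 36%.

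| d (trial SD) | 8 blocks | 4 blocks |
|---|---|---|
| 0.2 | 13% | 9% |
| 0.4 | 36% | 20% |
| 0.6 | 66% | 39% |
| 0.8 | 88% | 60% |

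**After matching.** If irrelevant trials are kept only where attention is in the opposite hemifield, both shares are 100% and the bias from d is 0. The minimum detectable difference at 80% power is (1.960 + 0.842) × √(1/n₁ + 1/n₂):

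- 8 blocks: 2.802 × √(1/96 + 1/192) = 0.35 pooled; 2.802 × √(2/96) = 0.40 matched.
- 4 blocks: 2.802 × √(1/48 + 1/96) = 0.50 pooled; 2.802 × √(2/48) = 0.57 matched.

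**What matching leaves.** With diagonal pairs only, the attended location on matched trials is the electrode's diagonal partner when ignored and its horizontal neighbour when irrelevant. The diagonal of a square is √2 ≈ 1.4 times its side, so distance and upper/lower field still differ by condition. Under upper-lower pairs no ignored trial has attention opposite and no irrelevant trial has it on the same side, so there is nothing to match.

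**The case against.** The strongest objection is that the bias needs an account the protocol does not pose. If alpha rises equally everywhere outside the selected region, irrelevant cortex on the attended side rises too, d is zero and there is no bias. If alpha rises only where targets were possible, ignored above irrelevant is a true finding. The spurious +d/2 needs a third account: a rise across one whole hemisphere, regardless of relevance. The cited lateralisation comes from scalp EEG, and the documents do not show that it holds at location-selective ECoG electrodes. All of this stands as a limit on size. It does not remove the point, because the third account is close to what Background and Significance describes and the planned contrast cannot rule it out.

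Four stronger readings are tempting but not supported:

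- A reader might infer that the ignored location always has a fixed hemifield relation to the attended one and the irrelevant locations never do. That fails for upper-lower pairs, where both relations are fixed. Because opposing is undefined, the sign of the bias is not settled either.
- A reader might infer that the plan prescribes pooling all irrelevant trials. It gives no model or pooling rule. It names attentional condition and is silent on hemifield.
- A reader might take the 96/96/192 split as general. It covers single-quadrant electrodes over 8 blocks. With diagonal pairs, an electrode covering both quadrants of one hemifield has one quadrant irrelevant whenever the other is attended or ignored, and the plan does not say how to classify it.
- A reader might conclude that the data would be unusable. With pairs that cross the midline, the matched trials are already in the planned data, so the analysis can recover the contrast.

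**Conclusion.** The concern holds in a conditional form. With diagonal or left-right pairs, balanced cueing and a single-quadrant electrode, attention is in the opposite hemifield on 100% of ignored and 50% of irrelevant trials. The contrast as planned therefore cannot separate a relevance effect from hemispheric lateralisation. The bias is +d/2, with d not given in the documents; the rejection rates above are illustrations under assumed values. Other readings of opposing change its size and sign, down to −d for upper-lower pairs only.

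This should be fixed, but it is not fatal. It affects the stated critical comparison of a preparatory sub-study, whereas the protocol's Specific Aim concerns unattended memory items. For midline-crossing pairs the remedy is prespecification. An analyst could split the trials later without it, but a split chosen after seeing the data carries less weight.

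**What to change.** In Research Design and Methods, Sub-study A, define the cued pairs as crossing the vertical midline (diagonal or left-right, never upper-lower). State the block sequence and the split of green within a pair.

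In Statistical Considerations, Sub-study A:

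- Prespecify the critical contrast as ignored versus irrelevant on trials where the attended location is in the hemifield opposite the electrode's preferred location.
- Report same-hemifield irrelevant trials as a separate condition.
- Limit the contrast to electrodes whose preferred location is a single quadrant, or state how electrodes responsive to several locations are classified.

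**Cost.** No extra patients or testing time. The irrelevant cell falls from 192 to 96 trials at 8 blocks and from 96 to 48 at 4 blocks, with the loss of sensitivity shown above.

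**Remaining limit.** If pairs are diagonal only, the plan must say that distance and upper/lower field still differ between the matched cells, and the conclusion must be limited accordingly. One option within the same definition is to use both diagonal and both left-right pairs, two blocks each. Each pair then has 2 × 48 = 96 trials, 48 per cue direction. Each matched cell has 48 trials with attention at the diagonal location and 48 at the horizontal neighbour, which balances both features. The hemifield matching would still be needed.
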